## 1.4 SIGNIFICANCE

The protocol is conceptually innovative in multiple aspects:

- The principal rationale for the trial is innovative as it targets mechanistic underpinnings, i.e. mitochondrial energetics and vascular function, as integral means to foster physical function, PA, and to diminish fatigability.
- The application of oral nitrite supplementation is innovative. While seminal literature regarding nitrite focuses predominantly on vascular effects, our pilot data raise important perspectives regarding its intrinsic effects on skeletal muscle mitochondria, which are the source of over 90% of adenosine triphosphate (ATP) needed for movement. Age-related changes in skeletal muscle mitochondrial function likely contribute to functional decline.
- We will use high-resolution respirometry to examine the activity of electron transport system (ETS) in permeabilized intact muscle fibers from freshly collected muscle specimens. This allows us to assay ETS function in a highly controlled ex vivo experiment at the myocellular level, removed from other potentially limiting physiological factors including supplies of substrates and oxygen. Specifically, we will use an Oroboros Oxigraph 2k to interrogate mitochondrial ETS function when reducing equivalents are channeled via complex I, complex II or electron transfer flavoprotein (fatty acids). This method preserves mitochondrial reticulum structure and function, which avoids erroneous mitochondrial dysfunction observed in isolated mitochondria and will complement in vivo assessment of mitochondria.
- Mitochondrial energetic capacity (ATPmax) will be determined by (phosphorus-magnetic resonance spectroscopy [P-MRS]) of the non-dominant quadriceps muscle. ATPmax incorporates all aspects of mitochondrial content and function including oxygen consumption, efficiency, and Ca2+ handling, all working together to produce ATP.
- The molecular underpinnings of improved skeletal muscle mitochondrial energetics will be determined via transcriptional RNA transcriptionomic profiling (RNA-seq), expression of key proteins (Western blots), and immunohistology (fiber type, capillary density).
- The skeletal muscle mitochondrial assessments will be coupled with an analysis of platelet mitochondrial energetics (Seahorse) to determine the utility of platelet measurements to be applied as (1) a novel and convenient biomarker of mitochondrial energetics.
- NIRS will be used to assess: (1) skeletal muscle mitochondrial metabolic performance profile during the hypoxic stress by gauging perfusion changes pre- and 12-week post-nitrite versus placebo. Clinical and Physiological assessments:

Fitness and Efficiency (1) CRF (peak VO2) on a progressive intensity cycle ergometer will clarify how changes in mitochondrial respirometry translate into systemic oxygen utilization, highlighting physiological linkage between cellular respiration and whole-body oxygen utilization and putative benefits of nitrite to improve these relationships; (2) VO2 at 60%-80% exercise resistance (watts) on a cycle ergometer until exhaustion will assess nitrite-mediated changes in endurance; (3) VO2

at a steady-state walking (1.5 mph) will assess nitrite-mediated changes in the efficiency of walking and associated perceived fatigability (changes in rated of perceived exertion); (4) 400-meter corridor walk (with portable gas exchange) will be used to assess overall capacity (disability), physical fatigability (slowing of walking speed), as well as the energy of walking.

Additional functional measures: (1) short physical performance battery (SPPB) to assess strength, balance, and an index of frail; (2) handgrip to assess strength; (3) daily activity (accelerometry).

Fatigability: Fatigability assessments are novel, and include both “perceived” (rate of perceived exertion [RPE]) during steady-state walking, as well as “performance” (energy consumed during a 400-meter corridor walk) subtypes.

## 2. RESEARCH DESIGN AND METHODS

### 2.1 CLASSIFICATION AND METHODOLOGICAL DESIGNS

We will conduct a prospective, randomized, placebo-controlled, double-blinded trial to study the utility of a 12-week intervention (oral nitrite capsules vs. placebo) in older (age  $\geq 70$  years) healthy, sedentary adults (<1 hour of structured PA per week). The primary aims of this protocol are to demonstrate the utility of chronic nitrite treatment to enhance (1) mitochondrial energetics, (2) vascular perfusion and (3) to explore whether physiological improvements translate to clinical enhancements (physical function, physical activity, fatigability).

### 2.2 DETAILED DESCRIPTION OF STUDY DESIGN

#### Study Procedures and Visits:

Study Visits and procedures will take place in the UPMC Magnetic Resonance Research Center (MRRC), UPMC Montefiore Translational Research Center (TRC), University of Pittsburgh Geriatric Research Center (GRC), or UPMC Kaufmann at the University of Pittsburgh Pepper Center– Senior Mobility Aging Research Training (SMART) Center and UPMC Emphysema/COPD Research Center.

Water and snacks will be available to participants throughout non-fasting visits. Participants will be provided a meal during fasting visits

#### Reminder Calls:

Study staff will call participants to remind them of study visit details, and of medications hold plans. The study staff will remind participants to hold medications per their anti-platelet and anti-coagulation medications hold plan at reminder calls for Visit 4 and Visit 9. Participants with diabetes who are on hypoglycemic medications will be advised if they need adjustments to their usual regimen for fasting and functional testing visits. Participants with diabetes will be asked to bring their own glucometer to assess glucose as needed. If a participant does not provide their own glucometer, a study glucometer will be available.

#### 2.2.1 Study Procedures and Assessments

##### Consent Visit

1. Obtain written informed consent using standardized procedures.

2. Medical histories will be obtained prior to the visit. At the study visit, details about the participants' medical histories will be reviewed. PI or a study clinician will evaluate the participants. Participants will be instructed to notify the study staff if there are any health or medication changes during their participation in the study. The Charlson Comorbidity Index and the Pittsburgh Fatigability Scale will be administered.
3. Weight, height, and vital signs (temperature, blood pressure (BP), heart rate (HR), respiratory rate (RR), SpO2). BP will be re-measured if it is initially outside of the inclusion range. This allows for common clinical variations attributable to anxiety, dehydration, timing of medications, and other factors.
4. Screening blood work by trained study staff will be completed be completed after consent and before randomization. See Study Timeline 2.2.2

**5. *7-Day Home Activity Monitoring:*** Participants will be issued an accelerometer (ActiGraph) non-invasive wrist monitoring device to be worn for a full 7 days following visit to assess changes in daily activity, including level/intensity of activity and sleep. Serial assessments by ActiGraph over the weeks of the protocol provide key data to gauge changes in physical activity that may result from nitrite supplements over time. Participants will receive instruction in the use of the ActiGraphs and asked to maintain an ActiGraph physical activity/sleep diary for the days that they are wearing the device. Participants will be reminded to return their ActiGraph at the visit following their 7-day wear.

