4. Skeletal Muscle Biopsy #1: Participants will lie comfortably in the supine position for biopsy of the vastus lateralis muscle of the non-dominant leg. Biopsy sites will be disinfected with chlorhexidine, lidocaine will then be administered to biopsy site. The physician investigator or study clinician will then make a small incision in the skin and insert a needle into the vastus lateralis to remove approximately 150 mg of muscle. Additional passes of the needle may be necessary for an adequate muscle sample. The wound site will be closed with Steri-strips™ (or a suture if subject is allergic to Steri-strips™) and a sterile pressure bandage.
  - a. Muscle specimens will be immediately processed and stored. Muscle specimens will be divided into portions for specific analyses. Any extra tissue will be stored for future analyses.
  - b. The biopsy wound will be compressed and dressed.
5. Randomization: Subject will be randomized following review of the participant safety status by PI.
6. Pharmacokinetics (pK)
  - a. Nursing staff will measure BP, RR, HR, SpO2, and MetHb to ensure subject is at a steady-state before administering the study drug. Baseline assessments of nitrite/nitrate will be collected. Participants will receive their first dose of study drug (20 mg Nitrite vs. Placebo). Then, the following will be assessed: BP(orthostatic hypotension assessment), HR and MetHb, RR and SpO2 every 15 minutes for the 2 hours post-drug administration period per standard operating procedure. If high MetHb level or if subject is hypotensive or symptomatic, after the study drug is administered, the PI or study clinician will be informed and advise on plan for management.
7. Blood assessments:
  - a. Nitrite/Nitrate Serum Levels and other Research Bloods: baseline (before study drug), 30 minutes, 60 minutes
  - b. Platelet Mitochondrial Respirometry: baseline (before study drug), 30 minutes
  - c. Research Inflammatory Indices: baseline (before study drug)
  - d. Heparinized blood will be immediately centrifuged at bedside to separate plasma and red cells and then flash frozen for future analyses. Total volume of blood drawn for 3 samples will be about 80 ml (about 5.4 tablespoons).
8. Skeletal Muscle Biopsy #2 immediately after the 30-minute blood sample is drawn.
9. A breakfast will be provided after the skeletal muscle biopsy #2.

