10. If the study drug is well tolerated, the PI will be contacted and IDS orders for enough study drug/placebo will be ordered to sufficiently cover dosing for participants as described in drug distribution section.
11. Drug supply dispersal

- a. Participants will receive sufficient study drug/placebo supply. We will instruct participants to return all of the study drug packaging, including unused study drug and empty packaging at each study visit and/or at the time of discontinuation from treatment.
12. Study staff will review medication administration and use of the drug diary card with all participants. Participants will be asked to record the time they take the drug each day and any symptoms with severity rating and/or health events during the dosing period.
13. The study staff will review biopsy site care with participants and if indicated, remind participants to resume their normal anti-coagulation/anti-platelet/anti-diabetic medications.
14. Participants will be called 2 days after biopsy for assessment of biopsy healing. All participants will be given the option of returning for an Interim Visit for direct assessment if symptomatic.
15. Daily activity: Participants will be encouraged to begin or extend a daily walking routine with specific instructions and encouragement to progress in time and length as tolerated.

In order to track these changes over the course of the 12-week intervention, participants will be asked general questions about activity level, exertion level, and barriers to activity. Furthermore, the study nurse will ask about any progress as part of the interim study on-site and phone-based assessments.

The Daily Activity questions are not a study endpoint, but rather they are pragmatic tools to encourage motivation and behaviors of activity. Only the ActiGraph data are study endpoints.

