## 2.2.2 Study Timetable

Study Phase	Pre-Drug Assessments					Midway Assessment	Post-Drug Assessments			
	Consent Visit	Visit 1	Visit 2	Visit 3	Visit 4		Visit 6	Visit 7	Visit 8	Visit 9
Approximate Time between Study Visits		Same day to +30 days	Visit 1 +1 day to ±14 days	Same day to +7 days	Previous Visit +1 day to ±14 days	6 weeks ±5 days	6 weeks ±5 days	Visit 6 days ±14 days	Same day to +7 days	Previous Visit to ±14days
Approximate Duration of each visit	1-2 hours	3-5 hours	3-4 hours	1-2 hours	3-4 hours	1-2 hours	3-4 hours	3-4 hours	1-2 hours	3-4 hours
Fasting prior to arrival					X	X				X
Consent	X									
Medical History	X									
Physical exam	X	X	X	X **	X	X	X	X	X **	X
Vital Signs	X	X	X	X						
Vital Signs with Methemoglobin					X	X	X	X	X	X
Max CPET*		X					X			
Sub-Max CPET*			X					X		
400-Meter Corridor Walk*#		X				X	X			
Steady-state walk*#			X			X		X		
SPPB			X			X		X		
Handgrip			X			X		X		
Home Actigraph	X	*					X			
Questionnaires	X	X					X			

3 Day Food Record (3DFR)**			X					X		
MRS				X					X	
Randomization					X					
Muscle Biopsies 1 & 2					X					X
Blood Draw Approximate total quantity	20 ml+				83 ml	81 ml	20 mL			81 ml
CBC	X+					X	X			
Complete Metabolic Panel (CMP)	X+						X			
25-hydroxy vitamin d (Vitamin D)	X+						X			
HbA1c	X+						X			
TSH	X+									
Nitrite/Nitrate					X	X				X
Inflammatory Indices					X	X				X
Additional Research Bloods					X	X				X

\*Assessment with NIRS

#Assessment with ActiGraph

+ Blood draw may be collected after signing consent and before randomization, blood draw may not include CMP and/or CBC/d if collected within the last 4 weeks

++ 3 Day Food Record distributed at Visit 1 and Visit 6 and collected from subject at Visit 2 and Visit 7

++ If deemed necessary

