#### **3.3 EXCLUSION CRITERIA**

- Blood pressure <110 or >160/95 mmHg
- Participant is at greater risk of hypotensive adverse events caused by sodium nitrate following review of past medical history and physical exam.
- Participants with GPD deficiency in whom sodium nitrate might increase the risk of hemolytic crisis.
- Orthopedic or other chronic condition which limits physical activity or exercise testing assessments
- If valve replacement has been performed, patient may not be enrolled for 12 months after this procedure
- Severe peripheral or pulmonary artery disease
- Anemia: Hgb <11.0 ( $\text{\textcircled{M}}$ ), 10.0 ( $\text{\textcircled{F}}$ ) gm/dl
- Participants with diabetes whose HgbA1c >10.0%

- Chronic alcohol (>14 drinks ETOH a week) or drug (any cocaine, methamphetamine, and cannabis ≥4 x week) dependency
- Allergy to lidocaine; Allergy to Red Dye
- Chronic use of oral corticosteroids or other medications that affect muscle function
- Current use of organic nitrates or phosphodiesterase type 5 (PDE5) inhibitors
- Unable to hold warfarin, direct-acting oral anticoagulants (DOACs), non-steroidal anti-inflammatory medications (NSAIDs) or aspirin for 3 days prior to muscle biopsy, or to hold thienopyridine medications for 5 days prior to muscle biopsy. Participants unable or unwilling to hold will follow the modified ASA hold plan
- Any bleeding disorder that would contraindicate biopsy such as history of clinically significant bleeding diathesis (e.g., Hemophilia A or B, Von Willebrand's Disease or congenital Factor VII deficiency)
- Unstable psychiatric diagnosis that would affect adherence and ability to complete the protocol
- Dementia or inability to give informed consent or follow study protocol
- End-stage disease
- Other chronic unstable disease such as active neoplasm, end stage chronic kidney, liver or other organ disease

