### Risk of lidocaine

This FDA-approved numbing medicine, lidocaine, is injected into the site before the biopsy procedure. Participants with prior difficulty with this local anesthetic will be excluded from the study. A possible side-effect is an anaphylactic reaction. Participants will be questioned before enrollment about prior experiences with the local anesthetic lidocaine. While the risks of having a reaction to lidocaine used for this purpose are rare, it is always possible to have an unexpected serious reaction to any medication.

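### Section 3.3 excludes G6PD deficiency because of hemolysis risk, but no G6PD test is scheduled, so only already-diagnosed cases can be kept off the drug

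*Combined protocol and SAP*

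**What the plan says.** All references are to the combined protocol and SAP.

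- **The exclusion.** Section 3.3 lists "Participants with GPD deficiency in whom sodium nitrate might increase the risk of hemolytic crisis". It gives no cutoff, does not limit itself to known cases, and does not say how the deficiency is to be found.
- **The screening draw.** Section 2.2.1, Consent Visit item 4: "Screening blood work by trained study staff will be completed be completed after consent and before randomization". The Section 2.2.2 timetable marks CBC, complete metabolic panel, 25-hydroxy vitamin D, HbA1c and TSH for it. A footnote repeats the timing ("Blood draw may be collected after signing consent and before randomization") and lets a recent CBC or metabolic panel stand in for a new one.
- **The check before dosing.** Section 2.2.1, Visit 4 item 5: "Subject will be randomized following review of the participant safety status by PI". The first 20 mg dose follows at the same visit.
- **On-treatment monitoring.** The timetable has a row "Vital Signs with Methemoglobin" from Visit 4 onward. Participants keep a diary of "any symptoms with severity rating and/or health events during the dosing period". The first scheduled on-treatment CBC is at Visit 5, six weeks ±5 days later.

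**The concern.** The protocol itself names hemolytic crisis as the reason to keep G6PD-deficient people off the drug. Yet the only routes it provides for finding them are medical history, record screening, physician referral or approval, and the PI's safety review. All of these depend on a diagnosis that someone has already made. A participant whose deficiency was never tested for could pass screening, be randomized, and receive nitrite three times daily. What is at stake is participant safety and whether the criterion does its job. No endpoint, sample size or analysis is affected.

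**Working it through.** The plan gives no figure on this point, so the check is mainly a comparison of sections, followed by the schedule arithmetic.

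**1. How comparable exclusions are ascertained**

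| Exclusion (Section 3.3) | Cutoff given | Means of finding it |
|---|---|---|
| Anemia | Hgb below 11.0 (men) or 10.0 (women) g/dl | CBC at screening |
| Diabetes control | HbA1c above 10.0% | HbA1c at screening |
| Hypotension risk | None | History and examination, stated in the criterion |
| Bleeding disorder | None | History, indicated in the criterion |
| Lidocaine allergy | None | Questioning (Section 6.1.2): "Participants will be questioned before enrollment about prior experiences with the local anesthetic lidocaine" |
| G6PD deficiency | None | Not stated |

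The G6PD line has neither a scheduled test nor a stated history route. No G6PD assay appears in any visit, in the timetable, in the risk section (6.1) or in the stopping section (10). The additional research bloods at Visit 4 are not itemized, but they are drawn on the day of first dosing and are not presented as eligibility tests.

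**2. Time and doses before the first scheduled on-treatment CBC**

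- Visit 5 is 6 weeks ±5 days after Visit 4: 42 − 5 = 37 days to 42 + 5 = 47 days.
- Dosing is three times daily (Section 2.3.4): 37 × 3 = 111 to 47 × 3 = 141 doses, assuming full adherence.
- Weekly calls completed in that time: 37/7 gives 5 whole weeks and 47/7 gives 6, so about 5 to 6 calls.

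**3. What the safeguards can detect**

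| Safeguard | What it covers | Identifies G6PD deficiency? |
|---|---|---|
| Screening Hgb cutoff | Removes people already clearly anemic | No |
| Two hours after first dose (Visit 4 item 6) | BP, heart rate, methemoglobin, respiratory rate, SpO2 | No |
| Call two days after the Visit 4 biopsy (item 14) | Biopsy healing, with an optional interim visit if symptomatic | No |
| Diary, weekly calls, 24-hour staff access | Symptoms | No |
| Interim visits (Section 10) | Methemoglobin; for lightheadedness or dizziness, also BP | No |

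Several of these could pick up a symptomatic event. None includes a scheduled hemoglobin measurement between the first dose and Visit 5.

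**4. Can the risk be sized?**

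The documents give no prevalence. Purely as an assumption, let the proportion p with undiagnosed deficiency run from 0.1% to 5%. The chance of at least one such person among the 35 allocated to nitrite is 1 − (1 − p)^35:

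- p = 0.1%: 3%
- p = 1%: 30%
- p = 5%: 83%

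The answer is set almost entirely by the assumption. It is also only the chance that such a person is present, not the chance of hemolysis, for which the documents give nothing.

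**5. Is there time for a result?**

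The visit windows put Visit 4 between 0 + 1 + 0 + 1 = 2 days and 30 + 14 + 7 + 14 = 65 days after consent. The baseline ActiGraph, issued at the Consent Visit, is "to be worn for a full 7 days following visit to assess changes in daily activity", so a completed baseline already needs about a week.

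**The case against.** The strongest reply is that the criterion means diagnosed deficiency and needs no test. Lidocaine allergy and bleeding disorders are handled by history, and no coagulation test is scheduled for the latter. On that reading the criterion and the screening agree. This is plausible, and for that reason the plan cannot be said to break its own rule. It does not help the undiagnosed, however, and the text does not say that only known cases are meant.

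Section 6.1.1 reports no adverse events in 80 nitrite-treated people (69 volunteers and 11 with sickle cell disease) on regimens described as 60–120 mg daily, against 3 × 20 = 60 mg here. That is reassuring in general. Because G6PD status is not stated, it says nothing either way about deficient people, and an upper limit computed from 0 of 80 should not be read as applying to them.

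Three stronger readings are tempting and are not supported:

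- *Only people who know their own status are excluded.* Section 5.1 provides for record screening, outside records and physician input, so a recorded diagnosis can be found even if the participant does not report it.
- *Participants are unmonitored until week 6.* The safeguards above are real, and Section 9.4 provides for review of safety data as they accrue.
- *The plan exposes participants to a demonstrated harm.* Section 3.3 says only that risk might increase, and the hematologic risk list in Section 6.1.1 names methemoglobinemia alone.

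It is also fair to say that the documents give no assay price or turnaround time. Low burden here means no added visit or procedure.

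**Conclusion.** The point holds as a gap in a safeguard. As written, the exclusion can be applied only to people already diagnosed, and an undiagnosed participant on nitrite could go 37 to 47 days without a scheduled hemoglobin check. The size of the risk cannot be estimated from the documents.

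This rests on three assumptions: that GPD means G6PD, which the hemolysis rationale supports; that no testing is specified in an operations manual outside these documents; and that full three-times-daily dosing starts at Visit 4. The change is worth making because it serves a hazard the protocol names and uses a blood draw already planned. It does not signify a statistical error or invalidate the design.

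**What to change.** 1. Add a G6PD assay, or accept a documented prior result, to the pre-randomization draw in Section 2.2.1, Consent Visit item 4, with a matching row in the Section 2.2.2 timetable. Draw it at the Consent Visit where possible.
2. State in Section 3.3 that a result in the laboratory's deficient range excludes.
3. Require the result in the PI's safety review at Visit 4 item 5, before randomization and first dose.
4. In Section 3.3, correct GPD to G6PD and nitrate to nitrite.
5. If a tube is added, update the blood volume in Section 6.1.2. It gives a maximum of about 224 ml, already below the timetable total of 20 + 83 + 81 + 20 + 81 = 285 ml.

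The cost is one assay per candidate without a prior result, possible screen failures, and a possible short wait before Visit 4. No extra visit is needed and the sample size does not change.

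If the sponsor intends to exclude diagnosed cases only, the smaller edit is to limit the criterion to known G6PD deficiency and say why testing is unnecessary. That aligns the criterion with the screening but leaves undiagnosed participants unprotected.
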